9.1.1 Spine-Related Cost of Care

Spine-related cost of care will be estimated by applying unit costs incurred by subjects or third-party payers to estimates of resource utilization obtained from subject-reported utilization data (Appendix H). Subject-reported utilization will be collected using monthly checklists for the first three months, then bimonthly for the following nine months, that are

based upon the approach recently employed by Fritz et al. (15) and originally developed by Goosens et al. (33). Subjects will be asked about all healthcare services used, including primary care visits, emergency room encounters, hospital admissions, imaging studies (including MR and CT), prescriptions, and physical therapy services that pertain to spine-related healthcare (14,34).

Data from the utilization checklists will be categorized using Current Procedural Terminology (CPT) and International Classification of Disease (ICD) codes. Medications will be characterized using the Unified Medical Language System® Master Drug Database, Medi-Span®.

Unit cost of these different services will be estimated using publicly available data sources. In specific, for outpatient visits to PCPs, specialists, physical therapists and other providers and for tests and procedures, we will use the Centers for Medicare & Medicaid Services Physician Fee Schedule Look-Up Tool.¹ For hospitalizations, we will use the hospital adjusted expenses per inpatient day value calculated by the Kaiser Family Foundation.² For emergency department visits, we will use estimates from the Medical Expenditure Panel Survey.³ To calculate the average retail price of medications, we will use average retail prices from GoodRx.com.⁴,

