5.2. Exclusion Criteria

- Patients with symptoms attributed to the spine but without actual pain in the spine (e.g. those with cervicogenic headache without neck pain)
- Currently pregnant
- Currently receiving disability benefits, worker's compensation, or involved in litigation for a workplace injury
- Currently enrolled in another intervention trial for the management of acute back or neck pain
- Cancer that is metastatic or being actively treated. (i.e., chemotherapy, radiation, surgery)
- History of receiving active therapy for back or neck pain in the past 3 months (7+ consecutive days of narcotic use, 6+ sessions of PT, chiropractic care, acupuncture, postural therapy, or other spine therapy delivered by a trained provider)
- History of spine surgery or spine injections/ablation in the past 6 months
- Severe, active psychosis or major depression inhibiting ability to physically participate in intervention
- Red Flag Symptoms (fever, night sweats, unintentional weight loss, bowel or bladder dysfunction, neurologic weakness, current intravenous drug use)

6. Interventions

Clinics will be randomized to one of the following three arms as described below.

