9.3 Data Collection

Study data will be collected and managed using REDCap electronic data capture tools (50) hosted at Brigham and Women's Hospital. Data will be collected based on the schedule in Table 3. Study subjects will be contacted by email five business days prior to a survey being due for completion to be notified that the survey is available. If the survey is not completed they will be notified again three and five business days after the due date. Should the study subject still not complete the survey, they will have three phone attempts to be reached and guided through completion.

Table 3: Subject Reported Outcome Administration Schedule

Metric	Months After Enrollment													
	0	1	1.5	2	3	4	5	6	7	8	9	10	11	12
STarT Back Tool	x													
Healthcare Utilization Checklist		x		x	x		x		x		x		x	x
Oswestry Disability Index	x		x		x			x						x

EQ-5D	x		x					x						x
Self-Efficacy Questionnaire	x							x						x

10. Statistical considerations

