10.1 Analysis plan

All analyses will be performed using intention to treat principles based on study arm with which a subject is assigned at study enrollment and regardless of whether or not all protocol steps have been completed. We will report means and frequencies of pre-randomization variables separately by study arm. Comparison of these values will be made with generalized estimating equations to adjust for the block and cluster randomized design.

Because cost data in healthcare is not normally distributed (32) due to significant zero data representing subjects for whom there is little to no cost, we will have to model the data accordingly. We will evaluate the two primary outcomes, total cost of care, using generalized estimating equations with gamma distributed errors and an identity link function which can account for a positively skewed distribution. Changes in ODI from baseline to three months will be compared for the treatment arms using generalized estimating with normally distributed errors and an identity link function. All models will adjust for age and sex, account for the cluster and block randomized study design and include fixed effects for the 3 different delivery networks that were used for recruitment. In secondary analyses, we will repeat our models adjusting for unmatched confounders that remained despite randomization. Our primary analyses will compare each of the two treatment arms separately with usual care (i.e., ICE compared with usual care and IPT with usual care). Because we are evaluating two primary

outcomes, we will use a Bonferroni-corrected two-tailed type 1 error of 0.025. Analysis of secondary outcomes will also be performed using generalized estimating equations with error distributions and link functions appropriate to the outcomes being evaluated.

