Missing data will be accounted for using multiple imputation (51), which has been determined an adequate strategy to minimize both false positive and false negatives in clinical trials. We will perform 20 imputations using Proc MI in SAS with a fully conditional specification. The following variables will be used to perform the imputation: age, study arm, study site, clinic, sex, race/ethnicity, BMI, exercise frequency at baseline, education level, employment status, smoking status, other medical conditions at baseline, number of medications used for spine pain at baseline, length of pain at baseline, number of previous pain episodes, STarT back score, baseline ODI, baseline self-efficacy, baseline EQ-5D, and scores for patient-reported outcomes at every follow-up timepoints (ODI, cost, Lorig self-efficacy scale, and EQ-5D).

As resource utilization and ODI were collected at multiple time points, we will also evaluate non-missing cost and ODI data from each time point using a repeated measures design. In specific, we will use generalized estimating equations, with link functions and error distributions appropriate to the study outcomes, to assess changes in outcomes over the 12 months of follow-up, while accounting for correlations in the repeated measurements. For spine-related health spending, these analyses will be conducted using the time intervals at which raw data were collected as well as after converting estimates to evenly-spaced months. Because cost data in healthcare is not normally distributed with zero values for participants with no resource utilization during follow-up, we will winsorize estimated costs at the 95th

percentile in secondary analyses. We will report relative spending differences with confidence intervals and a two-tailed p value. As a sensitivity analysis, we will conduct a complete-case analysis on all non-missing values.

Exploratory analyses will be performed evaluating the effect of the interventions on cost in various strata of clinical interest, including age, sex, STarT Back risk group, location of pain, and whether or not this was the subject's first pain episode. We will also evaluate the percentage of subjects in each arm with a decrease in ODI of six points at three, six, and twelve months of follow-up.

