10.2 Sample size

The ICE model was anticipated to reduce total cost of care by 25% compared to usual care (52–54). Because of the lack of peer-reviewed literature evaluating the economic impact of IPT, an effect similar to ICE was assumed for the purpose of performing power calculations. We will need to enroll a total of 3,096 patients (1,032 per arm) to conservatively detect a change in spending of 20% between either treatment arm and usual care with 80% power and an alpha of 0.05, with 33 clusters, and 10% loss to follow-up over the 12-month study period. Our results are robust to a standard deviation of 1.25 times the mean and an ICC value of 0.01. Given the substantially larger sample size required for our economic analyses, we powered our trial on the basis of this outcome, which would also give us more than 98% power to detect a 6-point change in ODI between each intervention arm and the usual care arm.

11. Risk Protection

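### Spine-related cost, the outcome that sets the sample size, has no baseline measurement on its own scale, so a cheap gain in precision and in protection against differential recruitment is forgone

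*Combined protocol and SAP*

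**What the plan says.** Protocol 9.1.1 and SAP 1.1 build one-year cost from subject reports made after enrolment: "Subject-reported utilization will be collected using monthly checklists for the first three months, then bimonthly for the following nine months". In Table 3 of Protocol 9.3, the row "Healthcare Utilization Checklist" has its first entry at month 1. The rows for ODI, EQ-5D and self-efficacy each have an entry at month 0. The SAP copy of the schedule agrees on both points.

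The imputation list in Protocol 10.1 (repeated in the SAP analysis plan) follows the same pattern. It names "STarT back score, baseline ODI, baseline self-efficacy, baseline EQ-5D", but no baseline cost. It also includes the count of spine-pain medications at baseline, the duration of pain and the number of previous episodes.

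The primary cost model adjusts for age, sex, the cluster and block design, and delivery network. A secondary analysis will adjust for confounders still unbalanced after randomization, but does not name them.

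On sample size, Protocol 10.2 says of cost that "we powered our trial on the basis of this outcome". The target is "to conservatively detect a change in spending of 20% between either treatment arm and usual care with 80% power and an alpha of 0.05", assuming "a standard deviation of 1.25 times the mean and an ICC value of 0.01". The analysis plan tests at a different level: "we will use a Bonferroni-corrected two-tailed type 1 error of 0.025".

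**The concern.** A baseline value of the outcome is usually the best single covariate for that outcome. Here the most variable outcome, with an SD above its mean, is the one that lacks it.

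The design adds a second reason to want one. Clinics are randomized (7.1), the trial is open label, and subjects consent when they present at a clinic whose arm is already assigned (7.3). Under 7.5, ICE and IPT subjects pay nothing out of pocket for study visits, while usual-care subjects pay their normal copayments. Willingness to enrol could therefore differ by arm in ways linked to healthcare use. Blocking uses patient volume, location and services offered, not prior spending. If the arms differed in prior spine-related cost, the planned data would not show it on the cost scale, and the primary model could not correct for it.

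The entry criteria do ask about recent treatment ("History of receiving active therapy for back or neck pain in the past 3 months"), but as thresholds: a subject with no physical therapy sessions and one with five both pass.

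**Working it through.** **Inputs from the documents.** Protocol 10.2: 1,032 per arm, 33 clinics (11 per arm under 1:1:1), 10% loss, 20% difference, SD 1.25 times the mean, ICC 0.01, alpha 0.05 (taken as two-sided; the section does not say). Protocol 10.1: analysis alpha 0.025, two-sided.

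**Assumed, not in the documents.** The correlation r between prior and one-year cost: 0.1 to 0.4. The baseline imbalance between arms: 0.1 SD.

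**Step 1: reproduce the plan's figure.** Work in units of the usual-care mean, with each arm's SD at 1.25 times its own mean.

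- Variances: 1.25² = 1.5625 and 1.5625 × 0.8² = 1.00; sum 2.5625.
- Before clustering: n₀ = 2.5625 × (1.960 + 0.842)² / 0.2² = 502.8 per arm.
- With 11 clinics per arm fixed: n = 502.8 × 0.99 / (1 − 502.8 × 0.01/11) = 917.
- With 10% loss: 917/0.9 = 1,019 per arm, against 1,032 stated (1.3% lower).

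A common SD in both arms gives 1,525 and alpha 0.025 gives 1,501, so neither reproduces the plan. The stated size thus follows with no baseline covariate.

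**Step 2: power as planned.** Completers per arm: 1,032 × 0.9 = 928.8.

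- Variance = 2.5625 × (0.99/928.8 + 0.01/11) = 2.5625 × (0.001066 + 0.000909) = 0.00506.
- SE = 0.0711; 0.2/SE = 2.81.
- Power is 80.3% at alpha 0.05 and 71.6% at 0.025.

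**Step 3: add a baseline covariate.** Multiply by (1 − r²) either the within-clinic term only (lower figure) or both terms (upper figure).

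| Assumed r | Power, alpha 0.05 | Power, alpha 0.025 |
|---|---|---|
| no covariate | 80.3% | 71.6% |
| 0.1 | 80.5–80.7% | 71.8–72.0% |
| 0.2 | 81.1–81.8% | 72.6–73.5% |
| 0.3 | 82.2–83.8% | 73.9–76.0% |
| 0.4 | 83.7–86.6% | 75.8–79.6% |

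The range is wide because the between-clinic term is 0.000909/0.001975 = 46% of the variance, and a subject-level covariate may or may not explain it.

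**Step 4: equivalent enrolment.** 3,096 × (1/(1 − r²) − 1) gives 129, 306 and 590 extra subjects at r = 0.2, 0.3 and 0.4. With 33 clinics fixed, extra subjects shrink only the within-clinic term, so these counts match the lower figures only. Reaching the upper 83.8% at r = 0.3 needs 0.99/n = 0.91 × 0.001975 − 0.000909 = 0.000888. That gives n of about 1,115 completers per arm, or about 620 extra enrolled.

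**Step 5: bias from an imbalance.** Shift = imbalance × r × 1.25. For 0.1 SD this is 0.1 × 0.1 × 1.25 = 1.25% of mean cost at r = 0.1, and 0.1 × 0.3 × 1.25 = 3.75% at r = 0.3. The latter is 3.75/20 = 19% of the target difference.

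Steps 3 to 5 are linear-model approximations. The planned cost model is gamma with an identity link in Protocol 10.1 and Poisson with a log link in the SAP.

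**The case against.** Four points on the other side carry weight.

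- **Power.** A reader might infer that the trial has lost part of its stated power. It has not. The 80% reproduces without a baseline covariate, so only a possible gain is forgone.
- **Adjustment.** A reader might also infer that prior use cannot be adjusted for at all. The documents do not support that. Medication count is itself a measure of prior use. Pain duration, previous episodes and STarT Back score are related to it, baseline variables are compared by arm, and a secondary adjusted analysis is planned. These remain proxies: none records earlier imaging, emergency visits or therapy sessions, and none is named in the primary cost model. The baseline and screening forms in the appendices are not reproduced in the text, so further items on prior use cannot be ruled out.
- **Size of r.** Section 5 limits pain to 3 months and excludes 7 or more consecutive days of narcotics or 6 or more therapy sessions in that time, and spine surgery or injections within 6 months. Much costly prior use is screened out, so r may be small. At r = 0.1 the gain is at most 0.4 points.
- **Need.** ODI is analysed as change and must have a baseline. One-year cost is a follow-up total and can be estimated without one.

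The imbalance of 0.1 SD is illustrative. Nothing in the documents shows that recruitment will differ by arm. These points limit the size of the issue but do not remove the gap.

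**Conclusion.** The gap is real, and its consequence is modest and uncertain. Cost lacks a baseline on its own scale, and its primary model contains no term for prior use. The related variables are reserved for imputation and, possibly, an unnamed secondary adjustment.

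At alpha 0.05 the forgone gain is under half a point of power at r = 0.1, about 2 to 4 points at r = 0.3 and about 3 to 6 at r = 0.4. It rests on an assumed r and a linear approximation. The protection against differential recruitment is worth having in this design, but its value cannot be quantified from the documents.

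For scale, sizing at 0.05 and testing at 0.025 is a separate matter. By the same method it costs 80.3 − 71.6 = 8.7 points, more than a baseline measure would recover at any r up to 0.4. This point is a recommended improvement with medium confidence; the plan is valid without it.

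**What to change.** If enrolment is still open:

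- Add the existing utilization checklist at month 0 in Protocol Table 3 and SAP Table 2, with a 3-month look-back matching the pain-duration limit and the therapy exclusion window.
- Price it with the same unit costs and report it by arm.
- Enter it, suitably transformed for skew, in the primary cost model in Protocol 10.1 and the SAP analysis plan, and add it to the imputation list.

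The cost is a short protocol and SAP amendment, a few more minutes of form filling before the visit, and reliance on 3-month recall.

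If enrolment is closed, as the final status, the 10-01-2021 date and the past-tense references to recruitment and data collection suggest, a month-0 form is no longer possible. Instead, amend the SAP to name medication count, pain duration, previous episodes, STarT Back score and baseline ODI as covariates in the primary cost model. That needs no new data, but should be fixed before cost is compared between arms. It recovers only what these proxies explain.

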9.1.2 Pain

The ODI is the most commonly used scale for low back pain (35). It is a self-administered questionnaire that has ten topics: intensity of pain, lifting, sexual function, social life, sleep, and ability to walk, sit, stand, care for oneself, and travel. It has been recommended as one of the standardized metrics for research of low back pain based on its ability to quantify functional

status in this population (36). The ODI typically takes three to five minutes to complete, and one minute to score (37). Previous studies have evaluated the ODI in pain-free subjects and found that mean score to be 10.19 (35, 38, 39) and those with disability from low back pain is 22.07 (40). Previous studies have indicated that a change in ODI by 6 points is clinically meaningful (41).

9.2 Other outcomes

9.2.1 Quality of Life

Quality of life will be assessed by the EQ-5D (Appendix I), which has been shown to be beneficial in describing and valuing health related quality of life (42, 43). It was developed for self-completion, and has been validated against other measures of quality of life, including SF-12 (44). The EQ-5D has been shown to correlate well with low back pain specific measurements, and also be responsive to change (45,46). The instrument consists of a descriptive section and a visual analogue scale. The descriptive section measures 5 dimensions of health (mobility, self-care, usual activities, pain/discomfort, anxiety/depression) with each dimension having 5 levels ranging from “no problem” to “extreme problem”. The visual analogue scale is a self-rated horizontal health scale with end points labelled as “the best health you can imagine” and “the worst health you can imagine”. The raw scores are converted into index scores based on US norms⁵. Previous studies identify a change in EQ-5D index of 0.08 as a minimal important clinical distance (47), and in a study evaluating the sensitivity to change of EQ-5D index with back pain it was seen that after two weeks there was a decrease of 0.21 after treatment; albeit this was in an interventional study that included steroid injections (46). The

EQ-5D is also helpful in converting to quality adjusted life years (QALY) to perform a cost utility analysis, and is the most common measure for conversion (37).

9.2.2 Self-Efficacy

We will evaluate self-efficacy at baseline, six months, and one year. As the focus of this trial is to support those with acute spine pain to prevent the development of chronic pain, measuring self-efficacy both as a predictor and outcome of the treatment arms will be necessary as a metric of self-management for future episodes. We will use Lorig et al.'s self-efficacy scale for individuals with musculoskeletal complaints, which has three subscales that focus on pain, functioning, and other symptoms (31). Because spine-specific pain is already captured with ODI, we will use the "functioning" and "other symptoms" subscales in this trial to measure self-efficacy (Appendix J). The "function" subscale produces an average of 73.27 (s.d. 20.22), and the "other symptoms" subscale produces an average of 55.62 (s.d. 21.64).

9.2.3 Productivity

We will also evaluate the impact of spine pain on work-related activities by evaluating absenteeism and presenteeism. Absenteeism will be assessed by subject self-report. Time lost from work, or other usual activities, associated with spine pain and all other health problems will be collected and measured. The total number of unplanned work absences will be multiplied by an average employee's daily wage to obtain the cost per participant of work absenteeism. Presenteeism will be assessed using the methods of van den Heuvel, et al (49). Three assertions will be ranked on a scale of 1-5: 1) I achieve all objectives of the job, 2) Job-

related tasks come easily to me, and 3) I perform well in my job. The scores will be dichotomized using the median value from all respondents. A study participant will be described as suffering from presenteeism if they are above the median value.

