2.3 Productivity

We will also evaluate the impact of spine pain on work-related activities by evaluating absenteeism and presenteeism. Absenteeism will be assessed by subject self-report. Time lost from work, or other usual activities, associated with spine pain and all other health problems will be collected and measured. The total number of unplanned work absences will be multiplied by an average employee's daily wage to obtain the cost per participant of work absenteeism. Presenteeism will be assessed using the methods of van den Heuvel, et al (49). Three assertions will be ranked on a scale of 1-5: 1) I achieve all objectives of the job, 2) Job-related tasks come easily to me, and 3) I perform well in my job. The scores will be dichotomized using the median value from all respondents. A study participant will be described as suffering from presenteeism if they are above the median value.

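### The presenteeism rule labels above-median scorers on positively worded performance items as impaired without stating the scoring direction, and its pooled median split discards information under either coding

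*Combined protocol and SAP*

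**What the plan says.** Protocol 9.2.3 and SAP 2.3, both headed Productivity, carry the same text. Presenteeism is to be assessed by the methods of a cited study, using three assertions, each scored 1 to 5: "1) I achieve all objectives of the job, 2) Job-related tasks come easily to me, and 3) I perform well in my job". The cut-point is the pooled sample median: "The scores will be dichotomized using the median value from all respondents". The label then follows: "A study participant will be described as suffering from presenteeism if they are above the median value".

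These sections do not state:
- which end of the 1 to 5 scale means agreement, or whether any item is reverse-scored;
- how the three items are combined into one score;
- at which visit the median is taken, and how scores equal to the median are treated.

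The administration schedules (protocol Table 3, SAP Table 2) have no productivity row. The section names no appendix for these items, whereas the ODI, the utilization checklist, the EQ-5D and the self-efficacy scale each have one. Presenteeism stands under the heading Other outcomes and is in neither the primary nor the secondary list. The analysis plan gives it no model of its own; the closest general statement covers secondary outcomes: "Analysis of secondary outcomes will also be performed using generalized estimating equations with error distributions and link functions appropriate to the outcomes being evaluated". No analysis of the undivided score is described.

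**The concern.** All three assertions describe doing the job well. On the most familiar convention for such items, a higher number means stronger agreement. Scoring above the median would then mean performing better than the typical respondent, and the rule would give those people the label meant for impaired performance. An intervention that improved work performance would be reported as increasing presenteeism.

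A second issue does not depend on the coding. Cutting a multi-level score at the sample median turns it into a yes/no variable, which costs precision. The overall share labelled impaired is then set by rank and by ties rather than by how impaired people are. If the median is recalculated at each visit, an improvement shared by all arms would not show.

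What is at stake is the sign and the precision of one declared outcome on work-related activities.

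**Working it through.** The plan gives no effect size, power or prevalence for presenteeism, so there is no stated figure to reproduce. The rule, the items and the pooled cut come from protocol 9.2.3 and SAP 2.3. The score distributions below are assumptions.

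**1. Direction.** Assume a normal score with SD 1, two arms of equal size, and a true improvement of d = 0.2 SD. The pooled median lies midway between the arm means, d/2 = 0.1 SD from each.

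- Share above the median in the arm with the higher mean: Φ(0.1) = 54.0%.
- Share above the median in the arm with the lower mean: Φ(−0.1) = 46.0%.

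| Coding | Improved arm labelled | Comparator labelled | Sign of the contrast |
|---|---|---|---|
| Higher number = agreement | 54.0% | 46.0% | reversed |
| 1 = full agreement, or items reverse-scored | 46.0% | 54.0% | correct |

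The documents do not say which row applies.

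**2. Information lost by the split, normal score.** A small shift d changes the proportion above the median by about d·φ(0), and the variance of a single yes/no value there is 1/4. Relative to the difference in means, the information kept is 4·φ(0)² = 4/(2π) = 2/π = 0.637. The loss is 1 − 0.637 = 36.3%, and the sample size needed rises by π/2 = 1.57.

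Check at d = 0.2, two-sided 0.05, 80% power, ignoring clustering:
- undivided score: 2(1.960 + 0.842)²/0.2², which rounds up to 393 per arm;
- split, 54.0% against 46.0%: 618 per arm, and 618/393 = 1.57;
- power of the split with 393 per arm: about 61%. A comparison with 90% power on the score falls to about 73%.

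**3. Information lost, coarse score.** The real score would be built from three 1 to 5 items, so ties matter. Sums of three items (range 3 to 15) were simulated from one latent normal factor, with cuts at −1.5, −0.5, 0.5 and 1.5 and a latent shift of 0.2 between arms. Respondents strictly above the pooled median were compared with the rest.

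| Latent mean | Inter-item correlation | Median | Above median | At median | Loss |
|---|---|---|---|---|---|
| 0 | 0.4 | 9 | 46.7% | 16.5% | 34.9% |
| 0 | 0.6 | 9 | 46.9% | 15.2% | 35.3% |
| 0.5 | 0.4 | 11 | 38.1% | 16.8% | 35.9% |
| 0.5 | 0.6 | 11 | 39.5% | 15.1% | 36.7% |
| 1.0 | 0.4 | 12 | 45.3% | 17.5% | 32.8% |
| 1.0 | 0.6 | 12 | 46.5% | 15.5% | 31.1% |
| 1.5 | 0.4 | 14 | 26.2% | 24.0% | 43.6% |
| 1.5 | 0.6 | 14 | 31.8% | 20.6% | 35.6% |

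The loss runs from 31% to 44%, and is 31% to 37% in seven of the eight scenarios.

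**4. Meaning of the prevalence.** By definition no more than half of respondents can lie strictly above their own pooled median. In the table the share labelled moves between 26% and 47% with the response pattern and the ties at the cut. The overall figure therefore cannot be read as the frequency of impaired work performance.

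**The case against.** The strongest reply is that the plan delegates scoring to a cited method and says only that the items are ranked from 1 to 5. It never says that 5 means agreement. If 1 means full agreement, above the median picks out the worse performers and the rule is right as written. This stands. A reader might infer that the trial will report presenteeism with the wrong sign; the documents do not support that, because the anchors and the survey form are not in the text. They show only that the label cannot be verified.

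The second reply is that the median split belongs to the plan's account of the cited method, and that a common cut is needed to compare arms, which a pooled median supplies. This stands in part. The pooled cut limits the overall share labelled but leaves the difference between arms free, so it would be wrong to infer that the split invalidates the comparison. The loss of information remains.

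The third reply is that the efficiency figures rest on assumed distributions and that no power is claimed for this outcome. That is correct. The figures describe what the split costs under stated assumptions and contradict no power claim in the plan.

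Finally, the document is titled final, is dated 10-01-2021, and refers to the collection of utilization and ODI data in the past tense. Stating the coding is a clarification, but changing the analysed form of the outcome at that stage may be post hoc and would have to be labelled so.

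**Conclusion.** The point holds in conditional form. Both documents attach the presenteeism label to above-median scores on positively worded items without giving the anchors or the scoring direction, and no other section settles it. If higher numbers mean agreement, the better performers are labelled impaired and the arm contrast is reversed (54.0% against 46.0% at an assumed 0.2 SD benefit). If 1 means full agreement, or items are reverse-scored, the label is correct. The text does not justify going from may be reversed to is reversed.

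Under either coding, the split discards about 36% of the information if the score is roughly normal, and 31% to 44% in the assumed three-item scenarios. It also caps the share labelled at about half, so the prevalence has no absolute meaning. The contrast between arms remains interpretable once the coding is known.

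Importance is low. This is one of the other outcomes, with no stated power, and no primary or secondary conclusion depends on it.

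**What to change.** 1. Check the coding on the survey form and state it in protocol 9.2.3 and SAP 2.3: the anchors of the 1 to 5 scale, any reverse-scoring, and how the three items are combined.
2. Make the label match the coding. If higher means agreement, presenteeism is below the median. If the items are coded or reversed so that higher means worse performance, above the median can stay.
3. Make the mean or sum of the three items the presenteeism outcome, analysed by GEE with an identity link and with the same adjustment for clustering, blocks, age, sex and delivery network as the plan's other models.
4. Keep the dichotomy as a supportive display. State which visit supplies the median and how scores equal to it are classified.
5. If the change is made after outcome data were seen, mark it as post hoc.

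The cost is a few sentences in each document and one extra model. It needs no new data if the three items were recorded individually, which should be confirmed because neither administration schedule lists them.
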